- Patients with score of ≥ 4 on the NIDA modified ASSIST for illicit opioids (e.g. heroin) OR a score of ≥ 4 on the NIDA modified ASSIST for prescription opioids
- Currently have a phone
- Able to provide a phone number and one additional piece of contact information

b. Exclusion Criteria:

- They are incarcerated or under arrest
- Non-English speaking
- Live beyond a 50 mile radius of HMC
- Require active resuscitation in the ED or other clinical area at the time of RA approach
- Are receiving palliative care services or hospice care for a chronic illness such as metastatic cancer
- Are in the ED or hospital for a primary psychiatric emergency such as suicidal ideation or attempt

- Receiving chronic opioid therapy (COT) defined as prescription opioids for most days out of the last 90 days for a chronic pain condition
- In the ED for sexual assault

3. Recruitment and Retention Estimates

Estimates for the recruitment plan are based on literature related to feasibility studies. Specifically, the sample size of this pilot is related to the pragmatics of recruitment and a sample of n=30 for each group is related to the necessity for examining feasibility including rates of refusal for each group as well as retention in both arms.⁸ Previous work by the research team delivering collaborative care from the ED for patients with injury and prescription drug misuse (ED-LINC 1.0) described excellent recruitment and retention rates of > 80% over six months for subjects getting the intervention.⁹ Therefore the study intends to recruit at least 30 participants per arm with retention rates at each assessment and/or follow-up time point of 80%.

III. STUDY PROCEDURES

A. EMR pre-screen OR staff referral

The study team will be accessing and obtaining PHI from the HMC electronic medical record (EMR) to determine if patients have risk for opioid problems or opioid use disorder. Specifically, each morning a member of the study team will review the current census of patients in the ED and first determine if they are eligible based on criteria listed above easily obtainable (e.g. age, chief complaint) by looking at the track shell using FirstNet. Next, the study team member will look at the EMR for possible eligible participants to see if one of the following items exists in the EMR which are associated with an increased risk of opioid use disorder based on literature:

- Previous overdose
- Diagnosis of OUD in the problem list

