Patient-reported outcomes will be assessed at 1, 3 and 6 months after the ED visit. Length of the follow-up interviews varies and is estimated that the shortest interview may take about 15 minutes to complete and up to 60 minutes to complete the longest follow-up assessment depending on subject answers. Subjects will be remunerated for their time. The study team will be flexible with regard to completion method of the follow-up interviews. The study team intends to complete follow-up interviews with subjects primarily in-person at Harborview Medical Center or other convenient public location or over the phone. Responses will be entered into REDCap. If scheduling time with an interviewer is difficult, a subject may also have the option of completing the follow-up assessment through the encrypted REDCap app or web-based platform, or by another preferred method (e.g., faxed interview, hardcopy mailed to their residence). If a subject is completing the assessment on their own, the interview form (e.g., PDF, hardcopy, REDCap) would not include their name or any directly identifying information. Subjects will be given explicit instructions on certain assessments such as the timeline follow back (TLFB) in order to complete this with accuracy and without RA/RC assistance. Subjects will be reminded they should complete the interview in a private space where no one else can have access or see the interview.

Some subjects will have difficulty completing the entire interview, such as due to fatigue. The study team will allow for patients who are unable to tolerate a full-length interview the option of completing an interview over multiple sessions

Prior observations from the study team's effectiveness implementation spectrum investigations suggest flexibility is also required with regards to the timing of outcome assessments. Biostatistical considerations related to power encourage obtaining follow-up assessments, even if the actual assessment date deviates from the planned outcome assessment point. The study team will attempt follow-up on the appropriate date (e.g., within 30 days for the one month follow-up interview) but understand that flexibility on timing of followup interviews are needed.

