Additionally, the study team anticipates about 20% attrition for follow-up interviews in this population. Missing or being unable to complete a follow-up interview is a common event and will not be counted and/or reported as a protocol deviation. This information will be documented and reported. If a subject misses a particular assessment, they are still able to complete subsequent assessments. This may occur if a subject is unreachable for several months or becomes incarcerated during the follow-up portion of the study.

At baseline, being a prisoner (i.e., incarcerated or taken in to custody immediately after discharge) falls under the exclusionary criteria for study participation. However, a subject may become incidentally incarcerated during the follow-up period. Study team members may become aware of a subject's change in incarceration status via public records search or from alternate contacts. The study team does not directly contact or collect any information from subjects while they are incarcerated. However, in accordance with the UW Prisoner SOP, section 8.3.2.4, the study may resume follow-up (and intervention, if applicable) activities with subjects who have incidentally become prisoners during the course of their trial participation once they have been released. The study team intends to search public jail records to track if patients have become incarcerated and when they are released in order to facilitate contacting them for subsequent study interviews.

B. End of Study Participation

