Unanticipated Problems. In general, unanticipated problems include any incident, experience, or outcome that meets **all** of the following criteria:

- 1) **unexpected** (in terms of nature, severity, or frequency) given (a) the research procedures that are described in the protocol-related documents, such as the IRB-approved research protocol and informed consent document; and (b) the characteristics of the subject population being studied;
- 2) **related or possibly related** to participation in the research (in this guidance document, *possibly related* means there is a reasonable possibility that the incident, experience, or outcome may have been caused by the procedures involved in the research); and
- 3) suggest that the research **places subjects or others at a greater risk of harm** (including physical, psychological, economic, or social harm) than was previously known or recognized.

AE and SAE Identification

The study population is known to experience a number of AEs and SAEs, as defined by OHRP that are not expected to be study-related. For instance, prior investigation by the research group with this population suggests that as many as 50% of subjects report "thoughts that they would be better off dead or of harming themselves in some way" over the course of the six months after their ED visit (See Appendix C for Participant Suicidality Safety Protocol). Overdose is also common in a population of

patients with risk for opioid use disorder and in previous work by [name] and others approximately 25% of patients in the HMC ED at high risk for opioid overdose had an overdose event (e.g. non-fatal or fatal) within 3 years. The study population often suffers from comorbid medical conditions pre-dating and possibly exacerbated by the ED visit and thus is likely to experience recurrent hospitalizations. Additionally, the study population is known to experience a high rate of incarceration.

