Past 30-day substance use will be obtained at baseline and every follow-up assessment and calendar will be used to track substance use on specific days. Prior to performing this assessment, members of the study team will receive training on TLFB methods including a webinar published by NIDA, review of the methods with current NIDA CTN project coordinators that have performed these assessments for a variety of substances in a variety of settings including the ED and will practice obtaining this data with practice participant encounters. This training will be completed prior to study start to ensure accuracy of obtaining this data. Episodic shadowing by study PI will be done to ensure there isn't drift of accuracy in data collection. TLFB data will be captured on a hard copy calendar and transferred to RedCap by study staff. The hard copy will not contain any PHI and be labeled with a study ID and will be kept in a locked cabinet in a locked

office. At least 25% of these forms will be double-entered into RedCap to ensure accuracy of data entry.

- **Health Care Utilization**

Emergency department (ED) utilization will be assessed throughout the duration of the trial using either the UW EMR system (e.g., the UW Amalga data repository) or the Emergency Department Information Exchange (EDIE) web-based platform on an approximately monthly basis. Additionally, EDIE data will be pulled for all consented patients to capture all ED visits, inpatient visits and any available outpatient visits from five years before enrollment up to five years after enrollment in the trial.

- **ED-LINC Intervention and Usual Care**

The study team will document ED-LINC intervention activities in REDCap. These notes are not static and are modifiable over the course of the trial. For instance, information may be added or modified as a consequence of supervision discussion. The study team will review documentation during team meetings and case conference supervisions and update notes as needed to provide the most complete and accurate picture of what transpired. The data logging tool in REDCap allows administrators to track these types of historical changes. REDCap records the date, time, username of the person logged in at that time, the type of event and the changes that were made. This audit trail in the data logging tool stores every entry/change throughout the life of the database which will help the study team check completeness of intervention data.

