Follow-up Completion Rates were calculated for each followup timepoint and were calculated as the number of participants that completed follow-up divided by the total number of participants randomized to each arm of the trial. The 6-month followup completion rate is shown as the number of participants that completed the 6-month self-report interview divided by the number of participants randomized to each arm.

ED-LINC Intervention and usual Care process Outcomes were determined from extensive research notes. Specifically the EDLINC interventionist conducted a process validity assessment and documented the number of unique ED-LINC elements completed for each participant in the intervention.

Implementation Appropriateness was calculated by providing this validated self-report measure to each participant randomized to the ED-LINC assessment. Results were dichotomized to calculate the frequency of participants who 'agreed' or 'completely agreed' that the intervention was 'applicable' and 'seemed like a good match' to document appropriateness.

Satisfaction was calculated using a validated satisfaction questionnaire and provided to all participants at six-months. Each participant will complete the questionnaire and their results will be summed. The median and IQR range will be calculated for participants in each group that complete the assessment.

Perception of Care Coordination will be done using questions from a validated scale. The Wilcoxon Rank Sum test will be used to determine if there are significant differences between groups.

Secondary Outcome Measures

Substance Use

Substance use will be measured using the timeline follow back procedure which is a validated calendar method to determine days of use in a certain calendar period. First, we will sum days of use of illicit opioid use in 30 days at baseline and each followup period for each participant. The mean days of use/30 days with an associated standard deviation will be calculated at each time-period for both the ED-LINC intervention and the usual care control groups.

Next, we will evaluate variance of the data and test model fit on unadjusted data using different distributions. Given previous work, we anticipate the data to be skewed and zero-inflated. Thus, we hypothesize that we may use a normal Gaussian, Poisson or negative binomial distribution.

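### Baseline and follow-up means of opioid-use days describe different groups once about 20% are lost, and neither the summary nor the planned regression corrects for it

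*SAP*

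**What the plan says.** The SAP (Secondary Outcome Measures, Substance Use) sums illicit-opioid days over 30 days for each participant, and then: "The mean days of use/30 days with an associated standard deviation will be calculated at each time-period", separately for ED-LINC and usual care. Next it compares distributions (Gaussian, Poisson, negative binomial). It ends with a reverse stepwise linear regression of clinician-selected variables together with intervention and TLFB time point, with elimination at p > 0.05. It gives no denominator, analysis set, missing-data rule or sensitivity analysis for this outcome.

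The protocol supplies the rest:

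- Data source (VII.B.2, Substance Use and TLFB): "Past 30-day substance use will be obtained at baseline and every follow-up assessment".
- Schedule (III, Follow-up Interviews): "Patient-reported outcomes will be assessed at 1, 3 and 6 months after the ED visit".
- Expected loss (same section): "the study team anticipates about 20% attrition for follow-up interviews in this population". This matches the 80% retention intended at each time point in II.B.3.
- Missed assessments (same section): a participant who misses one may still complete later ones. Of missing one, it says: "This may occur if a subject is unreachable for several months or becomes incarcerated during the follow-up portion of the study". It adds: "The study team does not directly contact or collect any information from subjects while they are incarcerated".
- Incarceration (V.A, AE and SAE Identification): "the study population is known to experience a high rate of incarceration". No rate is given.

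**The concern.** A row of arm means over time invites the reader to take the change from baseline as change in the participants. That is safe only if those interviewed at follow-up have the same mean use as the full cohort. Being unreachable for months and being in custody are hard to treat as unrelated to opioid use by default, yet unqualified means depend on that.

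The regression does not remove the problem. The SAP names no participant-level term or correlation between a participant's repeated measurements. Nothing obliges the model to keep baseline days, so its time effect compares the same shifting groups.

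At stake is the only secondary outcome in the SAP. The protocol (II.A) expects this pilot to inform later studies of ED-LINC, so the apparent change in use may be carried forward.

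**Working it through.** **Inputs.** Loss d = 0.20 (protocol, Follow-up Interviews). Arm size is 30 (protocol, II.B) or 20 (SAP, Summary of Clinical Trial Features). The documents give no mean or standard deviation (SD) for days of use and no description of those lost, so those values below are assumptions.

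**1. Consistency of the plan's own figure.** There is no power calculation to reproduce, because the sample size is set on pragmatic grounds. 1 − 0.80 retention = 0.20 attrition, so the two protocol figures agree. They leave 30 × 0.8 = 24 or 20 × 0.8 = 16 interviewed per arm.

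**2. Who is in each mean.** TLFB days come only from assessments, and no rule fills gaps, so each follow-up mean is an available-case mean. Each calendar covers 30 days and planned visits are at 1, 3 and 6 months, so on that schedule a missed window is not recovered at the next visit. Because participants can return after a miss, the group averaged can differ at every follow-up.

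**3. Bias of the follow-up mean.** Let M be the full-cohort mean and L the mean of those lost.

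Observed mean = (M − dL)/(1 − d), so bias = −[d/(1 − d)] × (L − M).

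At d = 0.20, d/(1 − d) = 0.25. For illustration, take 20 participants with M = 15 (300 days in total), four lost, and nobody changing:

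| Assumed L − M | Observed mean | Apparent change |
|---|---|---|
| −5 | (300 − 4×10)/16 = 16.25 | +1.25 |
| 0 | (300 − 4×15)/16 = 15 | 0 |
| +5 | (300 − 4×20)/16 = 13.75 | −1.25 |
| +10 | (300 − 4×25)/16 = 12.5 | −2.5 |

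The change depends on L − M and not on the choice of M.

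**4. Between arms.** If d and L − M are the same in both arms, the two biases are equal and cancel. If loss is assumed to be 10% in one arm and 30% in the other, the multipliers are 0.1/0.9 = 0.111 and 0.3/0.7 = 0.429, a difference of 0.317. That gives a spurious arm difference of 1.59 days for L − M = 5 and 3.17 days for L − M = 10.

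**5. Limits without assumptions about those lost.** Missing values lie between 0 and 30 days. If C is the mean of those interviewed, the full-cohort mean lies between 0.8C and 0.8C + 0.2 × 30 = 0.8C + 6. For C = 10 the range is 8 to 14 days. The 20% loss leaves each arm's mean open over 6 days.

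**The case against.** - **This is a pilot.** The protocol says it is not powered for differences (II.B.1) and that effect sizes are not being measured (VIII). Sampling error is also large. With an assumed half of participants at 25 days and half at 5 (SD 10), 16 per arm gives a standard error of 10/√16 = 2.5 days per mean and √2 × 2.5 = 3.5 for a difference. The illustrated bias of 1.25 to 2.5 days is no larger than one standard error of a mean. This stands, and it limits the consequence. But the printed SD conveys only spread among those seen and says nothing about this error.
- **Loss is already tracked and resisted.** Completion by arm at each time point is a primary outcome in the SAP. The protocol provides for alternate contacts, record searches, flexible timing and resumption after release. These measures may reduce the loss, but the 20% is what the protocol still expects in this population. Completion rates show how many were lost, not whether their use differed.
- **A regression follows the means.** True, and the means should not be read as the whole analysis. The gap is that the regression states neither within-participant structure nor a missing-data assumption.
- **Similar loss cancels between arms.** Correct. Differential loss is possible, since only ED-LINC has three months of care management and the study phone line, and the earlier retention figure in II.B.3 concerns people receiving the intervention. The documents give no usual-care retention figure, so this remains a possibility.

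**Conclusion.** The concern holds as a gap in the analysis plan. With 20% loss, the follow-up means describe a different group from the baseline mean, and the planned regression does not correct for it. The within-arm change is biased by 0.25 day per day of difference between those lost and the full cohort. The 5- and 10-day differences behind the 1.25- and 2.5-day figures are assumptions.

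A reader might infer that heavy users will be lost and that the trial will therefore show a false reduction. The documents do not support that: no section says those lost use more opioids, and if they use less the bias reverses. Nor do they attribute the 20% to incarceration or being unreachable, which are examples of why an assessment may be missed. A false advantage for ED-LINC does not follow either. The arm difference is biased only if the amount or kind of loss differs. If usual care lost more heavy users, its mean would fall and the comparison would turn against ED-LINC.

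The change is worth making, but for a secondary outcome in an unpowered pilot the consequence is moderate.

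**What to change.** 1. At each follow-up and in each arm, give n, the follow-up mean and the baseline mean of those same participants.
2. Show baseline days for those seen and those lost, by arm and time point.
3. Replace the stepwise linear regression with a likelihood-based repeated-measures model using the distribution chosen in the preceding step. Arm, time point and baseline days always stay in. All randomised participants with any TLFB data contribute, for example by treating baseline as one of the repeated outcomes, so that people never re-interviewed are not dropped. State the assumption: loss may depend on observed use but not, beyond that, on the unobserved days.
4. Because that assumption may fail, add a sensitivity range in which missing days are varied above and below the model's prediction, by arm. Carrying baseline forward as the only sensitivity analysis is not enough: it is one arbitrary value, and it assigns use from before the ED visit to people whose circumstances may have changed.

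The cost is revised SAP wording and a little more analysis. Baseline TLFB is already collected and follow-up completion is already tracked by condition, so no new data are needed. The results may be less favourable or less precise.

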further for eligibility using the participant eligibility summary (PES). Eligible participants will undergo informed consent procedures and a total of 60 participants will be randomized to the collaborative care intervention (n = 30) or care as usual (n =30) condition. Intervention activity will continue for three months after the ED visit, while follow-up continues for six months after the ED visit. Primary outcomes include feasibility. Secondary outcomes include substance use measured by days of use of opioids as well as utilization of healthcare services including ED visits, primary care visits, mental health visits and substance use treatment visits.

1. Aims and Hypotheses

- 1) The primary aim** of the investigation is to determine the feasibility of the collaborative care intervention initiated from the ED and delivered longitudinally. Taken together, all elements of the intervention are referred to as ED-LINC. Feasibility measures include enrollment rates, retention rates at each outcome and follow-up assessment, intervention completion rates and number and types of contacts made by the interventionist. Feasibility of implementation will also be assessed. Guided by Proctor's taxonomy of implementation outcomes⁷, acceptability, feasibility and fidelity to ED-LINC will be measured.
- 2) The secondary aims** of the study are to determine differences in substance use and health care utilization between the two arms. While the study is not powered to detect a difference as this is a feasibility pilot study, substance use and health care utilization will be measured. Specifically, substance use will be measured utilizing a time-line follow back calendar administered by the research assistant to determine days of heroin or illicit opioid use and days of prescription opioid misuse. Additionally, EDIE will be utilized to determine ED utilization and inpatient admissions across Washington, Oregon, Alaska and other areas that EDIE is active. Participants will provide self-report information on primary care visits, mental health and substance use treatment visits. Engagement in substance use treatment will be confirmed via phone by study staff at all periods of assessment.

2. Participants

a. Inclusion Criteria:

- Aged 18-65
- Patients with at least one risk factor for opioid use disorder via the EMR pre-screen

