I. STUDY IDENTIFICATION INFORMATION

TITLE OF PROTOCOL: Emergency Department Longitudinal Integrated Care 2.0 (ED-LINC 2.0)

PRINCIPAL INVESTIGATOR: [name] MD MS

FUNDER OF PROTOCOL: National Institute of Drug Abuse (NIDA)

CLINICALTRIALS.GOV: A description of this clinical trial will be available on <http://www.clinicaltrials.gov>, as required by U.S. Law. **NCT03699085**

SAP Version date: September 2021

Table of Contents:

Summary of Clinical Trial Features.....	Page 3
Primary Outcome Measures.....	Page 4
Refusal Rates	
Follow-up Completion Rates	
ED-LINC Intervention and usual Care process Outcomes	
Implementation Appropriateness	
Satisfaction	
Perception of Care Coordination	
Secondary Outcome Measures.....	Page 5
Substance Use	

Summary of Clinical Trial Features:

The *Emergency Department Longitudinal Integrated Care* (ED-LINC) intervention is a stepped collaborative care model of care initiated from the ED for patients with OUD that combines evidence-based treatment elements, proactive care coordination and population-level outcome tracking. ED-LINC builds upon previous work by tailoring the collaborative care model for patients at high risk for OUD presenting to the ED. A central objective of ED-LINC is to provide evidence-based treatment for OUD and related co-morbidity while in the ED in conjunction with proactive longitudinal care coordination that links patients to ongoing treatment. Weekly caseload supervision with measurement-based care outcome tracking allows for the stepping up of care for patients with recalcitrant symptoms, as well as opportunities to oversee care management linkages to community services targeting the key outcomes of initiation of MOUD and retention in MOUD treatment.

The main objective of this study was to conduct a pilot pragmatic randomized clinical trial of ED-LINC (n=20) compared to usual care (n=20) for ED patients at a single-site at high risk for OUD. The primary outcomes of this study pertain to feasibility of the model, research strategy and implementation.

Primary Outcome Measures

All primary outcome measures used **descriptive statistics**

Refusal Rate was calculated as the number of patients that refused or declined the self-report screening procedure in the ED divided by the eligible number of patients that could have done the self-report screening during the enrollment period.

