Once model fit is determined, a reverse stepwise selection will be performed using a linear regression of clinician-selected input variables, alongside the intervention and TLFB timepoint, and an elimination threshold of $p > 0.05$

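### The SAP's only regression model is built by backward elimination with no term protected, so the arm effect on opioid-use days can be dropped or, for small-to-moderate effects, reported too large

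*SAP*

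**What the plan says.** The modelling plan is at the end of the SAP, under Secondary Outcome Measures, Substance Use. It has three steps.

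- Days of illicit opioid use out of 30 are summarised as mean and SD by arm at baseline and at each follow-up.
- The analysts then "test model fit on unadjusted data using different distributions"; Gaussian, Poisson and negative binomial are the options, and skewed, zero-inflated data are expected.
- After that, "a reverse stepwise selection will be performed using a linear regression of clinician-selected input variables, alongside the intervention and TLFB timepoint", with "an elimination threshold of $p > 0.05".

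The SAP does not name the clinician-selected variables or limit them to baseline. It does not mention the randomisation stratum (prescription opioid misuse; protocol III.D), gives no method for several rows from one participant, and does not promise an arm estimate with a confidence interval. The only other between-arm inference in the SAP is a Wilcoxon test on perceived care coordination.

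The model serves the protocol's secondary aim (II.B.1) of comparing substance use between arms, of which the protocol says: "While the study is not powered to detect a difference as this is a feasibility pilot study".

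**The concern.** Backward elimination keeps a term only if it is significant in the data at hand. If the arm term is subject to that rule in a trial with little power, two things follow. A real but modest effect usually leaves the model, and an effect that stays has passed a significance filter, so it is too large on average. Its standard error also takes no account of the search that produced it.

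The secondary aim is to estimate a difference between arms. What a pilot can usefully offer on that aim is an estimate with an honest interval, reported whatever its p-value. A model estimate that appears only when significant would mislead anyone who uses it to plan a later study.

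A second weakness sits in the same sentence. Timepoint is in the model, so each participant can contribute rows at 1, 3 and 6 months, and possibly at baseline. An ordinary linear regression on those rows treats them as independent.

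**Working it through.** The documents give no effect size, SD or power for this outcome, so there is no planned figure to reproduce.

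**Inputs from the documents**
- Sample size in the SAP: "pilot pragmatic randomized clinical trial of ED-LINC (n=20) compared to usual care (n=20".
- Sample size in the protocol (II.B), used as a sensitivity case: "randomized to the collaborative care intervention (n = 30) or care as usual (n =30) condition".
- Attrition (protocol, Follow-up Interviews): "the study team anticipates about 20% attrition for follow-up interviews in this population". This gives 20 × 0.8 = 16 per arm at a visit.
- Follow-up at 1, 3 and 6 months; removal at p > 0.05, taken as two-sided.

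**Assumptions:** SD 12 days; true effect δ of 4 or 6 days (d = 4/12 = 0.33 and 6/12 = 0.5); within-person ICC ρ from 0.3 to 0.7.

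**Formula if arm can be removed.** Let c = 1.96 × the SE the model reports, s = the true SE, a = (c − δ)/s and b = (−c − δ)/s. Then
- P(kept) = [1 − Φ(a)] + Φ(b)
- mean estimate when kept = δ + s[φ(a) − φ(b)]/P(kept)

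**One row per person.** Here s equals the reported SE, 12√(2/n).
- At n = 20: s = 3.795 and c = 7.44, so an estimate below about 7.4 days is removed.
- For δ = 4: a = 0.906, b = −3.014, P(kept) = 0.1825 + 0.0013 = 0.184. Mean when kept = 4 + 3.795 × (0.2646 − 0.0042)/0.184 = 9.4 days.

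**Three pooled follow-up rows, 20% missing at each visit.**
- Rows per person average 3 × 0.8 = 2.4, or 48 per arm. Reported SE = 12√(2/48) = 2.449; c = 4.80.
- The mean square of rows per person is 0.48 + 2.4² = 6.24, and 6.24/2.4 = 2.6. The design effect is therefore 1 + 1.6ρ: 1.48 at ρ = 0.3 and 2.12 at ρ = 0.7.
- s = 2.449√1.48 = 2.98, or 2.449√2.12 = 3.57.

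| Setting | δ | Dropped | Mean when kept | Ratio |
|---|---|---|---|---|
| 1 row, 20 per arm | 4 | 82% | 9.4 | 2.3 |
| 1 row, 20 per arm | 6 | 65% | 10.0 | 1.7 |
| 1 row, 16 per arm | 4 | 84% | 10.3 | 2.6 |
| 1 row, 16 per arm | 6 | 71% | 11.0 | 1.8 |
| 3 rows, 20 per arm | 4 | 58–60% | 6.9–7.2 | 1.7–1.8 |
| 3 rows, 20 per arm | 6 | 34–37% | 7.7–8.1 | 1.3–1.4 |
| 1 row, 30 per arm | 4 | 75% | 7.9 | 2.0 |
| 1 row, 30 per arm | 6 | 51% | 8.5 | 1.4 |

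The formula leaves out the covariates. Simulations of the full backward elimination agree with it closely.
- One row, 4 days: dropped in 80–84%, averaging about 9.4–10.0 days when kept (up to 2.5-fold). Nominal 95% intervals of the kept estimates covered the truth in 68–84% of cases; at 6 days, in 85–89%.
- Three rows: 4 days dropped in 57–62% (7.1–7.3 days when kept); 6 days dropped in 37–39% (7.7–8.2 days when kept).

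**Large effects.** In simulations with one row and two prognostic covariates, d = 0.8 was dropped in 17% (20 per arm) to 29% (16 per arm), with 11–18% inflation. At d = 1.2 it was dropped in 1–5%, with 2–3% inflation. With three pooled rows, d = 0.8 was dropped in 8–12%, with 5–10% inflation.

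**If arm is forced in.** With one row per person and covariates still selected, simulated type I error is about 6–8%. It reached 9.5% in the least favourable cell (16 per arm, 10 candidates). The arm estimate is essentially unbiased.

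**Ignoring repeated rows, arm forced in.** Type I error from correlation alone is 2[1 − Φ(1.96/√DE)].
- Three rows: 2[1 − Φ(1.611)] = 11% at ρ = 0.3 and 2[1 − Φ(1.346)] = 18% at ρ = 0.7.
- If the baseline row is also pooled, rows average 3.4, the mean square is 0.48 + 3.4² = 12.04, and the design effect is 1 + (12.04/3.4 − 1)ρ = 1 + 2.54ρ. That gives 14% and 24%; adding covariate selection, simulation gives 17–29%.

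**The case against.** The strongest reply is that arm and timepoint are design variables that stand beside the pruned list and are never pruned. The word *alongside* permits that, and a reader who takes it as settled that arm will be eliminated goes further than the text. What stands against the reply is that no sentence protects any term, and the elimination threshold follows directly after a list that includes the intervention.

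A reader might also infer that the arm comparison would vanish. It would not: means and SDs by arm at every timepoint are reported before any modelling, and an approximate unadjusted difference and interval can be worked out from them. Those summaries do not, however, stop a selected model estimate from being quoted.

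Most of the dropping is simply low power. At d = 0.5 and 20 per arm, an ordinary pre-specified test is also non-significant about 65% of the time. That is true, but the ordinary analysis would still report its estimate and interval.

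It might further be inferred that any effect reported would be badly inflated with intervals too narrow, or that post-randomisation variables will enter the model. The first fails for large effects, as the figures show. The second rests only on the SAP's silence about which variables are eligible.

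Finally, the protocol says the study is unpowered, and its Interim Analysis section says effect sizes are not being measured. That limits the consequence. It does not justify letting a significance threshold decide whether the model shows a treatment effect.

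**Conclusion.** The defect is real and confined to the secondary substance-use model; it should be fixed. If arm is a candidate for removal, effects of 4 to 6 days are dropped in about 37–62% of trials with three pooled rows or about 65–84% with one row. When kept they are overstated about 1.3- to 2.5-fold. From d = 0.8 upwards the overstatement is small. If arm is always retained, selection itself costs little (type I error about 6–8%), and the larger problem is unmodelled within-person correlation (about 11–29%).

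These figures rest on an assumed SD of 12, the assumed effect sizes and ICCs, and normally distributed outcomes. The documents supply none of these, and actual use days are expected to be skewed. At the protocol's 30 per arm the pattern is the same but milder. The primary outcomes are descriptive feasibility measures and no conclusion about them changes.

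**What to change.** Replace the stepwise step with one pre-specified model:

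- Always retain arm, timepoint, baseline opioid-use days and the randomisation stratum (prescription opioid misuse).
- Name any further covariates in advance and restrict them to baseline measurements.
- Account for repeated measures within participant, for example with a mixed model, or with GEE and a small-sample correction.
- Report the arm estimate with its 95% CI whatever its p-value.
- Label any stepwise model already run as exploratory.

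The cost is a few lines of SAP text and one re-run of the model. What is given up is a covariate list chosen from the data.
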